16.4 REPEATED OR UNSCHEDULED ASSESSMENTS OF SAFETY PARAMETERS

If a patient has repeated assessments before the date of first dose of double-blind treatment period the results from the final nonmissing assessment made before the date of the first dose of double-blind investigational product will be used as baseline. If end-of-double-blind-treatment period assessments are repeated or if unscheduled visits occur, the last nonmissing postbaseline assessment during the double-blind treatment period will be used as the end-of-double-blind-treatment-period assessment for generating summary statistics. Likewise, if end of double-blind down-taper period assessments are repeated or if unscheduled visits occur, the last non-missing assessment during the double-blind down-taper period will be used as the end-of-double-blind-down-taper-period assessment for generating summary statistics. However, all postbaseline assessments will be used to determine PCS values for laboratory parameters, vital signs and ECG parameters, and to determine most severe suicidal ideation and most severe suicidal behavior from C-SSRS. All assessments will be presented in the data listings.

16.5 MISSING DATE OF THE LAST DOSE OF INVESTIGATIONAL PRODUCT

When the date of the last dose of investigational product in the study taken during the double-blind treatment period is missing for a patient in the Safety Population, all efforts should be made to obtain the date from the Investigator. If after all efforts are made it is still missing, the last available dosing record date will be used as the last dose date.

16.6 MISSING SEVERITY ASSESSMENT FOR ADVERSE EVENTS

If severity is missing for an AE that started before the date of the first dose of double-blind investigational product, an intensity of mild will be assigned. If severity is missing for an AE that started on or after the date of the first dose of double-blind investigational product, an intensity of severe will be assigned. The imputed values for severity assessment will be used for the incidence summary; the values will be shown as missing in the data listings.

16.7 MISSING CAUSAL RELATIONSHIP TO STUYD DRUG FOR ADVERSE EVENTS

If the causal relationship to the investigational product is missing for an AE that started on or after the date of the first dose of investigational product, a causality of yes will be assigned. The imputed values for causal relationship to investigational product will be used for the incidence summary; the values will be shown as missing in the data listings.

16.8 MISSING DATE INFORMATION FOR ADVERSE EVENTS

The following imputation rules only apply to cases in which the start date for AEs is incomplete (i.e., partly missing).

Missing month and day

- If the year of the incomplete start date is the same as the year of the first dose of study double-blind investigational product, the month and day of the first dose of double-blind investigational product will be assigned to the missing fields
- If the year of the incomplete start date is before the year of the first dose of double-blind investigational product, *December 31* will be assigned to the missing fields
- If the year of the incomplete start date is after the year of the first dose of double-blind investigational product, *January 1* will be assigned to the missing fields

Missing month only

• If only the month is missing, the day will be treated as missing and both the month and the day will be replaced according to the above procedure

Missing day only

- If the month and year of the incomplete start date are the same as the month and year of the first dose of double-blind investigational product, the day of the first dose of double-blind investigational product will be assigned to the missing day
- If either the year of the incomplete start date is before the year of the date of the first dose of double-blind investigational product or if both years are the same but the month of the incomplete start date is before the month of the date of the first dose of double-blind investigational product, the last day of the month will be assigned to the missing day
- If either the year of the incomplete start date is after the year of the date of the first dose of double-blind investigational product or if both years are the same but the month of the incomplete start date is after the month of the date of the first dose of double-blind investigational product, the first day of the month will be assigned to the missing day

If the stop date is complete and the imputed start date as above is after the stop date, the start date will be imputed by the stop date.

If the start date is completely missing and the stop date is complete, the following algorithm will be used to impute the start date:

- If the stop date is after the date of the first dose of double-blind investigational product, the date of the first dose of investigational product will be assigned to the missing start date
- If the stop date is before the date of the first dose of double-blind investigational product, the stop date will be assigned to the missing start date

16.9 MISSING DATE INFORMATION FOR PRIOR OR CONCOMITANT MEDICATIONS

For prior or concomitant medications, including rescue medications, incomplete (i.e., partly missing) start dates and/or stop dates will be imputed. When the start date and the stop date are both incomplete for a patient, the start date will be imputed first and then the stop date will be imputed. If the imputed started date is after the imputed stop date, the imputed stop date will be adjusted by imputed start date.

16.9.1 Incomplete Start Date

The following rules will be applied to impute the missing numeric fields for an incomplete prior or concomitant medication start date. If the stop date is complete and the imputed start date is after the stop date, the start date will be imputed using the stop date.

Missing month and day

- If the year of the incomplete start date is the same as the year of the first dose of double-blind investigational product, the month and day of the first dose of investigational product will be assigned to the missing fields
- If the year of the incomplete start date is before the year of the first dose of double-blind investigational product, *December 31* will be assigned to the missing fields
- If the year of the incomplete start date is after the year of the first dose of double-blind investigational product, *January 1* will be assigned to the missing fields

Missing month only

• If only the month is missing, the day will be treated as missing and both the month and the day will be replaced according to the above procedure

Missing day only

- If the month and year of the incomplete start date are the same as the month and year of the first dose of double-blind investigational product, the day of the first dose of investigational product will be assigned to the missing day
- If either the year of the incomplete start date is before the year of the date of the first dose of double-blind investigational product or if both years are the same but the month of the incomplete start date is before the month of the date of the first dose of double-blind investigational product, the last day of the month will be assigned to the missing day.
- If either the year of the incomplete start date is after the year of the date of the first dose of double-blind investigational product or if both years are the same but the month of the incomplete start date is after the month of the date of the first dose of double-blind investigational product, the first day of the month will be assigned to the missing day

16.9.2 Incomplete Stop Date

The following rules will be applied to impute the missing numeric fields for an incomplete prior or concomitant medication stop date. If the date of the last dose of double-blind investigational product is missing, impute it as descripted in Section 16.4. If the imputed stop date is before the start date (imputed or non-imputed start date), the imputed stop date will be equal to the start date.

Missing month and day

- If the year of the incomplete stop date is the same as the year of the last dose of investigational product during double-blind treatment period, the month and day of the last dose of investigational product will be assigned to the missing fields
- If the year of the incomplete stop date is before the year of the last dose of investigational product during double-blind treatment period, *December 31* will be assigned to the missing fields
- If the year of the incomplete stop date is after the year of the last dose of investigational product during double-blind treatment period, *January 1* will be assigned to the missing fields

Missing month only

• If only the month is missing, the day will be treated as missing and both the month and the day will be replaced according to the above procedure

Missing day only

- If the month and year of the incomplete stop date are the same as the month and year of the last dose of investigational product during double-blind treatment period, the day of the last dose of investigational product will be assigned to the missing day
- If either the year of the incomplete stop date is before the year of the date of the last dose of investigational product during double-blind treatment period or if both years are the same but the month of the incomplete stop date is before the month of the date of the last dose of investigational product during double-blind treatment period, the last day of the month will be assigned to the missing day
- If either the year of the incomplete stop date is after the year of the date of the last dose of investigational product during double-blind treatment period or if both years are the same but the month of the incomplete stop date is after the month of the date of the last dose of investigational product during double-blind treatment period, the first day of the month will be assigned to the missing day

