9.4.8 Prior and Concomitant Therapy

A list of concomitant medications that are allowed and not allowed for either episodic or chronic use is provided in [Appendix III](#). Medication history (psychotropic medication history during the previous 5 years and all other medications during the past 12 months) will be recorded at Visit 1 (Screening) in the eCRF. Thereafter, any changes in concomitant medications or new medications added will be recorded in the eCRF.

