8.0 DEMOGRAPHICS AND OTHER BASELINE CHARACTERISTICS

Demographic parameters (age; age group [7-11 and 12-17]; sex; race; ethnicity), and baseline characteristics (weight; height; and body mass index (BMI)) will be summarized descriptively by treatment group for the Safety and ITT populations, respectively. Baseline efficacy variables will be summarized by treatment group for the ITT population.

Continuous variables will be summarized by number of patients and mean, SD, median, Q1, Q3, minimum, and maximum values. Categorical variables will be summarized by number and percentage of patients.

Abnormalities in patients' medical and surgical histories will be coded using the *Medical Dictionary for Regulatory Activities (MedDRA)*, version 22.0 or newer. The number and percentage of patients with abnormalities in medical and surgical histories in each system organ class and preferred term will be summarized by treatment group for the Safety Population. MDD history and nondrug psychiatric treatment history will also be summarized by treatment group for the Safety Population.

The World Health Organization Drug Dictionary, version March 2017 or newer, will be used to classify prior and concomitant medications by therapeutic class and drug name.

Prior medication is defined as any medication taken before the date of the first dose of double-blind investigational product. Concomitant medication is defined as any medication taken on or after the date of the first dose of double-blind investigational product. Both prior and concomitant medications use will be coded by drug name and therapeutic class. The use of prior and concomitant medications will be summarized by the number and percentage of patients receiving each drug within each therapeutic class in each treatment group for the Safety Population. If a patient took a specific medication multiple times or took multiple medications within a specific therapeutic class, that patient would be counted only for the coded drug name or therapeutic class.

Summaries of concomitant medication use will be presented for the double-blind treatment period and the double-blind down-taper period, separately. Any concomitant medications started after the date of the last dose of double-blind investigational product in the study will not be presented in the summary tables but will be included in the patient data listings.

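### A medication with a year-only start in the first-dose year and a stop month before dosing is always counted as concomitant and never as prior, because SAP 16.9 to 16.9.2 move the recorded stop forward to the imputed start

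*SAP*

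**What the plan says.** The order and the tie-break are in SAP 16.9: when both dates are partial, "the start date will be imputed first and then the stop date will be imputed", and on conflict "the imputed stop date will be adjusted by imputed start date". Section 16.9.2 repeats the tie-break, for cases where an "imputed stop date is before the start date (imputed or non-imputed start date), the imputed stop date will be equal to the start date".

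Section 16.9.1 supplies the imputed start. With month and day missing, the trigger is "If the year of the incomplete start date is the same as the year of the first dose of double-blind investigational product"; the start then becomes the first-dose date. An earlier year gives 31 December of that year. A known month before the first-dose month gives the last day of that month. One safeguard pulls an impossible start back to the stop, but only where the stop date is complete.

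Section 16.9.2 gives a partial stop whose month precedes the last-dose month the last day of its own month. A year-only stop in the last-dose year gets the last-dose date.

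The classification is in SAP 8.0: "Prior medication is defined as any medication taken before the date of the first dose of double-blind investigational product". Concomitant means taken on or after that date.

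Protocol 9.4.8 sets what is collected at screening: "psychotropic medication history during the previous 5 years and all other medications during the past 12 months".

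For adverse events, SAP 16.8 imputes starts in the same way and has the same limited safeguard: "If the stop date is complete and the imputed start date as above is after the stop date", the start is replaced by the stop. SAP 11.1 identifies TEAEs by onset date.

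**The concern.** In one pattern an imputed value overrides a recorded one. The start month is unknown, so the first-dose date is a guess. The stop month is known and lies before dosing. The tie-break keeps the guess and discards the recorded month.

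The SAP also contradicts its own principle. With a complete stop, 16.9.1 lets the stop limit the start; with only the day of the stop missing, the priority reverses. One lost day-of-month turns a prior drug into a concomitant one.

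At stake are the by-arm prior and concomitant medication tables for the Safety Population. A psychotropic stopped before the trial would drop out of the prior table and appear among drugs taken during double-blind treatment, where exclusion 7 and Appendix III restrict such drugs. Through 16.8, an adverse event that ended before dosing could be counted as treatment-emergent.

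**Working it through.** **Inputs.** Imputation rules from SAP 16.9, 16.9.1 and 16.9.2; definitions from SAP 8.0. The plan states no figure to reproduce. The dates below are illustrative: first dose F = 21 Sep 2020, last double-blind dose 15 Nov 2020.

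**The rule as a formula.** Let S be the imputed start, E0 the stop as first imputed, and E the stop after the tie-break.

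- Start month missing, start year = year of F: S = F.
- Stop month known and before the month of F: E0 = last day of that month, so E0 < F.
- Tie-break: E = max(E0, S) = F.
- Prior requires S < F, which is false. Concomitant requires E ≥ F, which is true.

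The result does not depend on the particular dates.

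**Worked records.**

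| Recorded start | Recorded stop | Imputed start | Stop before → after tie-break | Class |
|---|---|---|---|---|
| 2020 | Jul 2020 | 21 Sep 2020 | 31 Jul → 21 Sep 2020 | concomitant only |
| 2020 | 15 Jul 2020 (complete) | 15 Jul 2020 | 15 Jul 2020, unchanged | prior only |
| Mar 2020 | Jul 2020 | 31 Mar 2020 | 31 Jul 2020, unchanged | prior only |
| 2019 | Jul 2020 | 31 Dec 2019 | 31 Jul 2020, unchanged | prior only |
| 2019 | Jun 2019 | 31 Dec 2019 | 30 Jun → 31 Dec 2019 | prior only |
| 2020 | 2020 | 21 Sep 2020 | 15 Nov 2020, unchanged | concomitant only |

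Row 1 is the error: the latest possible recorded stop, 31 July, is 52 days before first dose. Row 2 is the same course with the stop day known. In row 5 the stop is moved but stays before dosing, so the class is still right. In row 6 no stop is moved, and the record does not rule out use during treatment.

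**All patterns.** The rules were applied to every first-dose date in 2020, with start and stop years 2018 to 2020 and both dates partial, keeping only stops recorded in a month or year before first dose:

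- start in the first-dose year, month missing: 2,018 of 2,018 classed as concomitant and not prior;
- start in the first-dose year, month known: 0 of 8,752;
- start in an earlier year: 0 of 189,718.

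The 2,018 can be checked by hand: a first dose in month m leaves m − 1 earlier stop months in that year, and the sum over the 366 days of 2020 is 2,018. These are counts of date patterns, not expected frequencies.

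**Share of records.** The population here is records with a year-only start and a month-known stop. Assumptions: first dose spread evenly over the year; 200,000 simulated courses per scenario. Washout courses stop 7 to 35 days before first dose and start 14 to 365 days before that. Look-back courses have both dates placed at random in the stated period before a screening visit 7 days before first dose.

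| Scenario | Stop month before first-dose month (this error) | Stop in first-dose month | Total losing prior status |
|---|---|---|---|
| Washout | about 28% | about 15% | about 43% |
| 12-month look-back | about 29% | about 2% | about 31% |
| 5-year look-back | about 1% | about 0.1% | about 1% |

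Only the first results column belongs to this point. In the second, no stop is moved and the recorded month does not show a stop before dosing. Per 10 such records, the first column means about 3, 3 and 0.1 misclassified.

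**Adverse events.** Take start 2020, stop Aug 2020, F = 21 Sep 2020. The stop is not complete, so the 16.8 safeguard does not apply. Onset becomes 21 Sep 2020, which is 21 days after the latest possible recorded end, and SAP 11.1 counts a TEAE. The window is narrow. Protocol 9.5.2.1 collects adverse events from consent, and dosing starts the day after Visit 2, here 20 Sep. A usual screening period of at most 10 days starts no earlier than 10 Sep, so no August event is possible. The 5-week maximum (35 days) reaches back to 16 Aug.

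**The case against.** The strongest defence is that this is a corner of a descriptive table. No efficacy model in SAP 10.1 to 10.3 uses the prior/concomitant split. Important deviations, including concomitant medications, are reviewed before database lock under Protocol 9.7.2, and nothing says that prohibited use is judged from imputed dates. Affected records predate randomised treatment, so there is no reason to expect a difference between arms. Exclusion 7 requires sites to verify washout before Visit 2, so recent stops are the ones most likely to have complete dates, and the edit checks in Protocol 9.6.2 may query the rest. All of this stands and limits the consequence.

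It might also be said that calling an uncertain drug concomitant is the cautious choice. That does not stand here, because the record is not uncertain on the point that matters: its last possible stop precedes dosing.

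Four stronger readings are tempting and are not supported.

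- A reader might infer that any record with both dates partial is misclassified. The enumeration shows that only one pattern is.
- A reader might treat year-only start with year-only stop as a further error. That record is compatible with use during treatment, and no recorded information is overridden.
- A reader might quote 43% or 31%. Those totals include stops recorded in the first-dose month, which this mechanism does not produce.
- A reader might convert the shares into a patient count or infer confounding of the efficacy result. The documents give no frequency of partial dates, and for psychotropics spread over the 5-year history the share is about 1%.

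**Conclusion.** The written rules give a wrong class, without exception, for a medication whose start has no month and falls in the first-dose year and whose stop has a known month and year before the first-dose month. The conclusion follows from the text of SAP 8.0 and 16.9 to 16.9.2 and needs no assumption.

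The shares of about 28%, 29% and 1% do rest on the assumed course timings, and they apply only among records with a year-only start and a month-known stop. How many of those the trial holds is unknown.

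The effect stops at the descriptive prior and concomitant medication tables and, rarely, a TEAE count for a screening-period event. It does not reach the primary or secondary analysis. It is worth correcting because the error always runs in one direction, contradicts the SAP's own treatment of complete stops, and is cheap to remove.

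**What to change.** Keep the stop-date imputation in 16.9.2 and its last-dose anchor. Imputing every partial stop to the latest date it allows would push a year-only stop of 2020 to 31 December, past the last dose, and create a new error.

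Extend the 16.9.1 safeguard instead: *if the stop date is partial and the last possible date of its recorded month (or year) is before the imputed start date, the start date is set to that last possible date, and the stop-date adjustment in 16.9 and 16.9.2 is not applied.* With this, start 2020, stop Jul 2020 becomes 31 Jul to 31 Jul 2020, prior only. The year-only/year-only record is unchanged.

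Add the same limit to 16.8: an imputed adverse event start may not fall after the last possible date of a partially recorded stop.

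Cost: one or two SAP sentences and a small change to the date-imputation code, with no new data. A few prior and concomitant medication counts would change, and possibly a TEAE count.

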16.10 CHARACTER VALUES OF CLINICAL LABORATORY PARAMETERS

If the reported value of a clinical laboratory parameter cannot be used in a statistical summary table because, for example, a character string is reported for a parameter of the numeric type, a coded value must be appropriately determined for use in the statistical analyses. The actual values, however, as reported in the database will be presented in the data listings.

Table 16–3 shows examples of how some possible laboratory results should be coded for the analysis.

Table 16–3. Examples of Coding Special Character Values for Clinical Laboratory Parameters

Laboratory Test, SI Unit	Possible Laboratory Results	Coded Value for Analysis
CHEMISTRY	1 0551616 Euroratory Results	Coded value for ringing
ALT, U/L	< 5	5
AST, U/L	< 5	5
Bilirubin, total, μmol/L	< 2	2
URINALYSIS		
	< 2.775, Negative	0
	[2.775, 5.55)	1+
C1 1/5	[5.55, 13.875)	2+
Glucose, mmol/L	[13.875, 27.75)	3+
	[27.75, 55.5)	4+
	≥55.5	5+
1/1	$> 0.444, \ge 0.444, > 0$, Trace	Positive
Ketones, mmol/L	≤ 0, Negative	Negative
II	> 8.0, ≥ 8.0	8.0
pH	≥ 8.5	8.5
	< 0, Negative	Negative
	[0, 0.15), Trace	0
Dustain a/I	[0.15, 0.3)	1+
Protein g/L	[0.3, 1.0)	2+
	[1.0, 5.0)	3+
	≥ 5.0	4+

ALT = alanine aminotransferase; AST = aspartate aminotransferase; SI = *Le Système International d'Unités* (International System of Units).

